4.4.2.2.2 Intensity

Intensity will be derived according to the following classification:

None, Grade 1, Grade 2, Grade 3, or Missing (Unknown).

If the unsolicited AE is measurable and its preferred term is part of the list of solicited reactions, then the measurement is derived based upon and following the same rule as the intensity scales defined in the [Section 4.4.2.1.1](#) for that measurable injection site or systemic reaction. Note the intensity could be considered as "None" (not a reaction) in the analysis despite being considered a reaction by the investigator.

Intensity for the other unsolicited non-serious AEs will correspond to the value reported in the CRF. The maximum intensity corresponds to the highest intensity for a unique term.

4.4.2.2.3 Last Vaccination

Last vaccination before an unsolicited AE is derived from the start date of the unsolicited AE provided in the CRF and is calculated as follows:

- If an unsolicited AE has a complete start date and different to any of the vaccination dates, the start date is used to determine the last vaccination before the unsolicited AE.

- If the start date is missing or partially missing, or equal to any vaccination date, then the visit number in the “Appeared after Visit” or similar field, is used to determine the last vaccination before the unsolicited AE.

4.4.2.2.4 Time of Onset

Time of onset is derived from the start date of the unsolicited AE and the date of last vaccination as described in [Section 4.4.2.2.3](#):

Time of Onset = start date of the unsolicited AE - date of last vaccination before the unsolicited AE.

The time of onset is considered as missing only if one or both dates are missing or partially missing.

The unsolicited AEs will be analyzed “Within 30 days” after each vaccination, which corresponds to AEs with a time of onset between day 0 and day 30.

Unsolicited AE that occurred before vaccination (negative time of onset) will not be included in analysis but will be listed separately.

Unsolicited AE which is non-serious, non-AESI and non-MAAE that occurred with a time of onset higher than defined above will not be included in analysis but will be listed separately.

- For unsolicited AE with missing day, month and year, the unsolicited AE will be classified as “Within 30 days”
- For unsolicited AE with partially missing start date, the partial available information will be used to determine if this AE is classified “Within 30 days” or “Not within 30 days”. An AE will be categorized as “Not within 30 days” only if there is clear evidence from the partially missing start date that this AE happens before the first vaccination or after the last vaccination + 30 days. In all other situations, this AE is considered as “Within 30 days”. Situations may happen as:
 - If the start date of AE has missing Day and non-missing Month and Year:
 - If the “Month/Year of AE start date” < “Month/Year of first vaccination date”, then it is clear that this unsolicited AE happened before the first vaccination and this unsolicited AE will not be included in the analysis but will be listed separately.
 - Else if the “Month/Year of last vaccination date” <= “Month/Year of AE start date” <= “Month/Year of (last vaccination date + 30 days)”, then this unsolicited AE will be categorized as “Within 30 days”.
 - Else if the “Month/Year of AE start date” > “Month/Year of (last vaccination date + 30 days)”, then this unsolicited AE will be categorized as “not within 30 days”. If the AE is non-serious, non-AESI and non-MAAE, then it will not be included in the analysis but will be listed separately.
 - If the start date of AE has missing Day and Month and non-missing Year:
 - If the “Year of AE start date” < “Year of first vaccination date”, then it is clear that this unsolicited AE happens before the first vaccination and this

unsolicited AE will not be included in the analysis but will be listed separately.

- Else if the “Year of last vaccination date” <= “Year of AE start date” <= “Year of (last vaccination date + 30 days)”, then this unsolicited AE will be categorized as “Within 30 days”.
- Else if the “Year of AE start date” > “Year of (last vaccination date + 30 days)”, then this unsolicited AE will be categorized as “not within 30 days”. If the AE is non-serious, non-AESI and non-MAAE, then it will not be included in the analysis but will be listed separately.

A few examples of missing time of onset with start date of AE partially missing:

First injection date	Last injection date	Start date of the AE	Injection date + 30	Will be analyzed “Within 30 days” ?
16Oct2023	16Oct2023	Missing	N/A	Y
16Oct2023	16Oct2023	Sep2023	N/A	N
16Oct2023	16Oct2023	Oct2023	15Nov2023	Y
16Oct2023	16Oct2023	Nov2023	15Nov2023	Y
16Oct2023	16Oct2023	Dec2023	15Nov2023	N
05Jan2023	05Jan2023	2022	N/A	N
16Oct2023	16Oct2023	2023	15Nov2023	Y
08Dec2023	08Dec2023	2024	07Jan2024	Y
16Oct2023	16Oct2023	2024	15Nov2023	N

Time of onset period is displayed as D0-D3, D4-D7, D8-D14, D15 or later, and Missing.

Note: For project at a later stage, even if it's recommended to use the above rule, it's possible to follow the below rule, for homogeneity need:

The unsolicited AEs will be analyzed “Within 30 days” after each vaccination, which corresponds to Aes with a time of onset between day 0 and day 30 or missing .An AE with missing time of onset will be considered to have occurred just after the last vaccination (computed according to the [section 4.4.2.2.3](#)), so will be included in these tables.

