*This call is made 8 days after the respective vaccinations. If day 8 falls on a weekend or holiday, the telephone call may be made on the following business day. During this telephone call, the staff will find out whether the subject experienced any SAE (including AEIs) and/or MAAE not yet reported and will remind the subject's parent/guardian to continue using the diary card, to bring the diary card to the study center at the next visit, and confirm the date and time of the next visit.

†At Visit (V) 03, subjects must be at least 24 weeks of age (164 days), the minimum age for the final dose of HB in the vaccine series, and no more than 32 weeks of age (the maximum age for the 3rd dose of rotavirus vaccine administration).

‡Physical examination should be performed as per standard of care.

§Temperature needs to be measured before each vaccination and recorded in the source documents.

**Should a subject receive oral or injectable antibiotic therapy within 3 days prior to any blood draw, the investigator will postpone that blood draw until it has been 3 days since the subject last received oral or injectable antibiotic therapy. Postponement must still be within the timeframe for blood draw. If postponement would result in the sample collection falling outside of this timeframe, the blood sample should be collected without postponement, and it should be appropriately documented that the sample was taken less than 3 days after stopping antibiotic treatment.

††Blood sample will be drawn prior to vaccinations.

†††Physical examination should be performed on the basis of relevant medical history at the time of the visit according to the investigator's clinical judgment. Temperature needs to be measured before each vaccination and recorded in the source documents

§§Routine pediatric vaccines at V01: Pentacel[®], Prevnar 13[®], and RotaTeq[®]; at V02: Pentacel[®], Prevnar 13[®], and RotaTeq[®]; at V03: Pentacel[®], Prevnar 13[®], RotaTeq[®], ENGERIX-B[®]

***The diary card is used only for the recording of SAEs and medically-attended AEs from D31 after completion of the first year's vaccinations (V04) until the vaccination visit in the second year of life (V05). The subject's parent/guardian will bring the completed diary card to the study site at V05.

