By definition, solicited reactions are to be considered as being related to the product administered. The assessment of these reactions by the Investigator is mandatory. For injectable vaccines, solicited reactions can either be solicited injection site reactions or solicited systemic reactions.

Unsolicited AE / AR:

An unsolicited AE is an observed AE that does not fulfill the conditions prelisted in the CRB in terms of diagnosis and/or onset window post-vaccination. For example, if headache between D0 and D07 is a solicited reaction (i.e., pre-listed in the protocol and CRB), then a headache starting on D07 is a solicited reaction, whereas headache starting on D08 post-vaccination is an unsolicited AE. Unsolicited AEs includes both serious (SAEs) and non-serious unsolicited AEs.

Injection Site Reaction:

An injection site reaction is an AR at and around the injection site. Injection site reactions are commonly inflammatory reactions. They are considered to be related to the product administered.

Systemic AE:

Systemic AEs are all AEs that are not injection or administration site reactions. They therefore include systemic manifestations such as headache, fever, as well as localized or topical manifestations that are not associated with the vaccination or administration site (e.g., erythema that is localized but that is not occurring at the injection site).

Adverse Event of Special Interest (AESI):

AESI is an event for which ongoing monitoring and rapid communication by the Investigator to the Sponsor must be done. Such an event might warrant further investigation in order to characterize and understand it. Depending on the nature of the event, rapid communication by the study Sponsor to other parties (e.g., regulators) might also be warranted.

Medically-Attended Adverse Event (MAAE)

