4.3.2.3.5 Medically-Attended Adverse Events

MAAE information will be collected throughout the study. MAAEs will be recorded as unsolicited AEs for up to D30 after each vaccination and as MAAEs until the next study visit on the appropriate diary cards. MAAEs that occur from D31 after the last vaccination visit until the 6-month follow up phone call will be recorded as such in the appropriate memory aid. An MAAE that occurs within the study period but meets the definition of an SAE should be reported only on the SAE Reporting Form. The Investigator will assess the causal relationship between the MAAE and the investigational or study product as either “Not related” or “Related”, as described in [Section 4.3.2.3.6..](#)

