4.4.2.4 Medically-Attended Adverse Event (MAAE)

An event will be considered as a MAAE if “Yes” is checked for “Is the event an MAAE?” in the CRF.

MAAE will be analyzed during the following time periods:

- Within 7 days after vaccination
- Within 30 days after vaccination
- During the study (i.e., all MAAEs occurred during the study), including the 6-month follow-up period.

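### The Appeared-after-Visit field assigns the dose but not the 30-day window, so undated or ambiguously dated SAEs, AESIs and MAAEs can be counted within 30 days when that field shows later onset

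*SAP*

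**What the plan says.** Dose attribution is in SAP 4.4.2.2.3. When a start date is missing, partial or equal to a vaccination date, "then the visit number in the “Appeared after Visit” or similar field, is used to determine the last vaccination before the unsolicited AE".

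The window is decided in SAP 4.4.2.2.4. For a wholly missing date, "For unsolicited AE with missing day, month and year, the unsolicited AE will be classified as “Within 30 days". For a partial date, "An AE will be categorized as “Not within 30 days” only if there is clear evidence from the partially missing start date"; anything not excluded that way is within the window. SAP 5.4.1.4 sends unsolicited AEs with missing onset, SAEs included, through these two sections, and SAP 4.3.2.1 states that "Unsolicited AEs includes both serious (SAEs) and non-serious unsolicited AEs".

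The 30-day window is a reporting period for SAEs including AESIs (SAP 4.4.2.3) and for MAAEs (SAP 4.4.2.4: "Within 30 days after vaccination"). Table 5.5 also reports a period that starts at D31.

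Collection after D30 uses separate instruments. The SAP Table 3.3 footnote on DC4 reads "The diary card is used only for the recording of SAEs and medically-attended AEs from D31 after completion of the first year's vaccinations". SAP 4.3.2.3.5 adds, for the memory aid, "MAAEs that occur from D31 after the last vaccination visit until the 6-month follow up phone call will be recorded as such".

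**The concern.** The SAP trusts one field to say which dose an undated event follows, then does not consult it on whether the event could have started within 30 days of that dose. In this trial the field can be informative, because several visits give no vaccine and fall 30 to 51 days after a dose. The cards or memory aids handed out there collect only SAEs and MAAEs.

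An event coded as appearing after such a visit is linked back to the previous dose. If its date is missing or too coarse, it is then counted in that dose's first 30 days. The 30-day SAE, AESI and MAAE percentages would be somewhat too high and the later period correspondingly short.

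**Working it through.** **1. Inputs.**
- Window rule: SAP 4.4.2.2.4. Dose rule: SAP 4.4.2.2.3.
- V4 is V3 + 30 days (+21), so D30 to D51 (SAP Table 3.3). The same 30 (+21) day spacing applies to V6 after V5 in 1a/2a, V7 after V6 in 1b/2b, and V8 after V7 in 2a (SAP Tables 3.4 to 3.7).
- Instruments issued there for SAEs and MAAEs only: DC4 at V4 (all subjects), DC6 at V6 (2a), and memory aids at V6 (1a), V7 (1b/2b) and V8 (2a) (protocol 5.1.4).

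**2. The SAP's own examples.** Coded as written, the rule is:
- no date: within;
- partial date before the first vaccination: not within;
- partial date between the month or year of the last vaccination and that of last vaccination + 30 days: within;
- later: not within;
- anything else: within.

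The nine worked examples give Y, N, Y, Y, N, N, Y, Y, N, and all nine reproduce. In every one the first and last injection dates are the same, so none shows a multi-visit schedule.

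**3. A post-V4 event.** Assume V3 on 16 Oct 2023, so D30 = 16 Oct + 30 days = 15 Nov 2023. The V4 window is then 15 Nov (D30) to 6 Dec (D51). Take V4 on 20 Nov (D35) and an MAAE coded as appearing after V4.

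| Recorded start date | Possible onset, given the field | SAP result |
|---|---|---|
| Missing | D35 up to V5 | Within 30 days |
| 2023 | D35 to D76 (31 Dec) | Within 30 days |
| Nov 2023 | D35 to D45 (30 Nov) | Within 30 days |
| Dec 2023 | D46 to D76 | Not within 30 days |
| 2024 | D77 or later | Not within 30 days |

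The first three rows are misplaced; the last two are right. The V4 date does not enter the rule, so with V4 on 6 Dec (D51) an undated post-V4 event is still labelled within 30 days.

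**4. How much the date's precision matters.** Assume onset uniform from D31 to V5, averaged over V3 dates through one calendar year. The V3-V5 gap follows from the age windows, with 12 months taken as 365 days:
- shortest: 365 - 224 = 141 days;
- longest in Group 2: 395 - 164 = 231 days;
- longest in Group 1: 486 - 164 = 322 days.

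Share of true post-D30 events classed as within 30 days:

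| V3-V5 gap | No date | Year only | Month and year | Full date |
|---|---|---|---|---|
| 141 days | 100% | 85% | 13% | 0% |
| 231 days | 100% | 73% | 7% | 0% |
| 322 days | 100% | 60% | 5% | 0% |

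These shares apply among events with that level of date precision. They are not shares of all events, and they cover every post-D30 onset, including any before V4 that the field could not identify.

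**5. With the field as evidence.** An event coded after V4 cannot start before V4. If V4 is later than D30, the event is outside the window. If V4 falls exactly on D30, a same-day onset is D30 and inside it, so the default should stay.

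**The case against.** The strongest reply is that this is an openly stated conservative default. An event counts against the vaccine unless there is clear evidence otherwise, SAP 5.1.4 tests no safety hypotheses, and the events stay in the whole-study summaries. Onset tables have a missing category, and listings mark incomplete dates (SAP 5.4.1). That defence holds where timing is unknown. It is weaker where a field the SAP already relies on can show the timing, and the default is not conservative for the later period.

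A second reply stands as a limit. The SAP refers only to this field or a similar one, and the permitted values are not shown. If the form lists only vaccination visits, a DC4 event would read as after V3 and the change would do nothing, though no harm either. Nor does reporting on a later card prove later onset, since staff also ask about other events since the previous visit (SAP 4.3.2.3). The evidence must be the field, not the card.

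Third, incomplete dates may be few: start dates are to be recorded (SAP 4.3.2.3.3), sites must explain missing information (protocol 11.1) and SAEs are reported within 24 hours (protocol 10.1). Table 5.5 also does not plainly say where a V4-to-V5 event belongs, because its later period ends at the next visit, which after V3 is V4.

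A reader might infer that the SAP ignores the field altogether. It does not: the field assigns the dose for every missing or partial date. A reader might also infer that everything on the post-D30 cards lands in the 30-day window. Fully dated events and partial dates later than the month or year of D30 are placed correctly.

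**Conclusion.** The point holds in limited form. SAEs, AESIs and MAAEs with a wholly missing start date, or a partial date that cannot exclude D0-D30, are counted within 30 days even when Appeared after Visit names a non-vaccination visit more than 30 days after the last dose. Only the split between periods in descriptive safety tables changes. Whole-study totals, immunogenicity analyses and hypothesis tests are untouched.

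The number of affected events cannot be derived. It would need the event rate after these visits and the share of incomplete dates, and the documents give neither. A reader might infer a material distortion of the 30-day rates; nothing in the documents supports that. The conclusion assumes that the field can name a non-vaccination visit, which the case report form must confirm.

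**What to change.** In SAP 4.4.2.2.4, extend the clear-evidence condition so that evidence may come from the partial start date or from the Appeared-after-Visit field, and apply it to wholly missing dates as well. Then add:
- If the field names a non-vaccination visit (V4; V6 in 1a/2a; V7 in 1b/2b; V8 in 2a) whose actual date is more than 30 days after the last vaccination, classify the event as not within 30 days.
- Count such events in the after-D30 or follow-up period and in the whole-study period, and make clear in Table 5.5 which later period takes a V4-to-V5 event.
- Keep the within-30-days default for all other undated or ambiguous events, including when that visit falls on D30 or earlier, or when the field records only vaccination visits.

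The closing note of 4.4.2.2.4 permits a broader rule that places every missing onset in the window. The change works only if the recommended rule is the one programmed, so the SAP should say which applies.

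The cost is a few sentences and one programming condition on a field the SAP already uses. Trial conduct, endpoints and hypotheses do not change.

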5.4.1.4 Start Date and End Date

Missing or partially missing start dates or end dates for unsolicited AEs (including SAEs) will remain missing and not be imputed. If the start date is missing or partially missing, the time of onset will be considered to be missing. Nevertheless, unsolicited AEs with missing time of onset will be included in analyses within or not within the defined time window (according to the [section 4.4.2.2.4](#)), according to the last vaccination (computed according to the [section 4.4.2.2.3](#)). If either the start date or end date is missing or partially missing, the duration will be considered missing.

Missing or partially missing end dates for ongoing solicited AEs will remain missing and not be imputed.

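### SAP 4.4.2.2.4 recommends one rule for adverse events with partial start dates, but its closing Note permits a second rule that counts events shown to lie outside the 30-day window as inside it

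*SAP*

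**What the plan says.** SAP 4.4.2.2.4 computes time of onset as the AE start date minus the date of the last vaccination before it, and defines when that quantity is unavailable: "The time of onset is considered as missing only if one or both dates are missing or partially missing". So a start date known only to the month or year already counts as a missing onset.

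For these dates the section gives a detailed main rule. The known month or year is compared with the vaccination dates, and an AE is placed outside the window only where there is "clear evidence from the partially missing start date that this AE happens before the first vaccination or after the last vaccination + 30 days". If the partial date shows onset before the first vaccination, the "unsolicited AE will not be included in the analysis but will be listed separately". If it shows onset beyond day 30, the AE is classed as not within 30 days. A wholly missing date is classed as within 30 days. Nine worked examples follow.

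The section closes with a Note, addressed to projects at a later stage, which keeps the main rule as the recommended one but says it is "possible to follow the below rule, for homogeneity need". The rule that follows defines the 30-day window as onset from day 0 to day 30, or missing, and explains: "An AE with missing time of onset will be considered to have occurred just after the last vaccination".

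SAP 5.4.1.4, the missing-data section, says that "unsolicited AEs with missing time of onset will be included in analyses within or not within the defined time window", and refers back to 4.4.2.2.4 for the classification. SAP 5.8 records that 4.4.2.2.3, 4.4.2.2.4 and 5.4.1.4 were updated to a new version of the Standard Safety Tables. It does not say which of the two rules this trial uses.

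**The concern.** Two rules are on the page for the same derivation, and they disagree wherever a partial date is informative. The Note attaches no condition beyond a need for homogeneity and does not say whether this trial has that need. Protocol 12.1 expects the SAP to set out the conventions to be used, and an option left open does not do that.

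What is at stake is the content of the D0–D30 safety tables. Unsolicited AEs include serious ones. Serious AEs and medically-attended AEs (MAAEs) are summarised within 30 days (SAP 4.4.2.3 and 4.4.2.4) and, separately, from D31 to the next visit (SAP Table 5.5). Under the Note, an event that its own partial date places after day 30, or before any vaccine was given, would be reported as a post-vaccination event within 30 days.

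**Working it through.** **Inputs.** The definition of missing onset, the main rule, the Note and the nine example rows all come from SAP 4.4.2.2.4.

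**Main rule.** Let s be the known part of the AE start date (month and year, or year only), f the same part of the first vaccination date, and l the same part of the last vaccination date + 30 days.
- s wholly missing: within (Y)
- s < f: before vaccination, excluded (N)
- s > l: after day 30, not within (N)
- otherwise: within (Y)

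**Note rule.** Start date missing or partly missing means onset missing, so within (Y).

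Each example has a single injection date, so first and last vaccination coincide.

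| Vaccination | + 30 days | AE start | SAP table | Main rule | Note rule |
|---|---|---|---|---|---|
| 16Oct2023 | 15Nov2023 | missing | Y | Y | Y |
| 16Oct2023 | 15Nov2023 | Sep2023 | N | N: Sep2023 < Oct2023 | **Y** |
| 16Oct2023 | 15Nov2023 | Oct2023 | Y | Y | Y |
| 16Oct2023 | 15Nov2023 | Nov2023 | Y | Y | Y |
| 16Oct2023 | 15Nov2023 | Dec2023 | N | N: Dec2023 > Nov2023 | **Y** |
| 05Jan2023 | 04Feb2023 | 2022 | N | N: 2022 < 2023 | **Y** |
| 16Oct2023 | 15Nov2023 | 2023 | Y | Y | Y |
| 08Dec2023 | 07Jan2024 | 2024 | Y | Y: 2024 = 2024 | Y |
| 16Oct2023 | 15Nov2023 | 2024 | N | N: 2024 > 2023 | **Y** |

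The main rule reproduces the SAP's column in all nine rows (5 Y, 4 N). The Note gives 9 Y, 0 N. Four rows change: two after day 30 (Dec2023 and 2024, against 16Oct2023) and two before vaccination (Sep2023 against 16Oct2023; 2022 against 05Jan2023).

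**Where the rules agree.** With a complete start date the onset is a number, so both rules give the same window. A pre-vaccination AE is removed under either, because the section also says: "Unsolicited AE that occurred before vaccination (negative time of onset) will not be included in analysis but will be listed separately". With a wholly missing date both rules give Y. That exclusion depends on a negative onset, which cannot be computed from a partial date, so it does not rescue the pre-vaccination rows under the Note. The visit field used in 4.4.2.2.3 assigns such an AE to a dose; it does not remove it.

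**Where a changed AE would go.**
- After day 30, and neither serious, of special interest nor medically attended: listing only under the main rule; D0–D30 tables under the Note.
- After day 30, and serious, of special interest or medically attended: in whole-study summaries under both, but counted in D0–D30 rather than after D30 under the Note.
- Before the first vaccination: listing only under the main rule; D0–D30 tables under the Note.

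**Check against 5.4.1.4.** That section allows a missing-onset AE to fall inside or outside the window. Only the main rule can place one outside.

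**The case against.** The strongest reply is that the SAP already leans one way. The Note itself calls the main rule recommended, 5.4.1.4 is compatible only with that rule, and 5.8 shows that the three linked sections were revised together. On this view the Note is leftover template text. That is a fair reading and it limits the point. It does not dispose of it, because the Note remains a stated permission and nothing in the SAP withdraws it for this trial.

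Some stronger readings are tempting and should not be drawn.
- A reader might infer that pre-vaccination events in general would be counted as post-vaccination. Only partial dates earlier than the month or year of the first vaccination are affected. These should be rare: enrolment and first vaccination normally fall at the same visit, the first diary card is handed out after that vaccination, and pre-existing conditions are not AEs unless they worsen (Protocol 5.1.4.1, 6.4 and 9.3.2.1).
- A reader might infer that the rule will be picked after the data are seen. The documents do not say when the choice would be made. It is left unstated, nothing more.
- A reader might suppose that events between Visits 4 and 5 and in the 6-month follow-up rest on unaided recall and so are the most exposed. The Protocol provides a diary card for the first period and a memory aid for the second (5.1.4.1, 5.1.4.2 and 11.1).

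It is also fair to say that the alternative over-counts rather than hides events and applies to both groups, that the onset tables keep a category for missing values, and that safety is descriptive, with no hypothesis tested (SAP 5.1.4). For an AE with no date at all, counting it as post-vaccination is a reasonable cautious convention, and the main rule does the same. The difficulty is confined to dates that carry usable information.

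**Conclusion.** The point holds in a limited form. SAP 4.4.2.2.4 contains a recommended rule and an unconditional option to replace it with one that puts some AEs in the wrong window and conflicts with 5.4.1.4. The two rules disagree on four of the SAP's nine illustrative rows. Those rows were written to show edge cases, so four in nine is not an estimate of how many AEs in the trial would move. That number cannot be derived, because the documents give no frequency of partial dates. The realistic effect is that some late events would be counted in D0–D30; the pre-vaccination case is possible but should be uncommon.

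The conclusion assumes that the Note's reference to missing onset carries the section's own definition, which includes partly missing dates. The effect is limited to descriptive D0–D30 safety tables and does not touch the immunogenicity hypotheses. It is worth correcting because the text is wrong as it stands and the correction is nearly free.

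**What to change.** Delete the Note and its alternative rule from SAP 4.4.2.2.4, so that the partial-date rule is the only one and agrees with 5.4.1.4. Repeating the cross-reference to 4.4.2.2.3 for the last vaccination within the individual branches is optional. The opening of the section already gives it, though the worked examples are all single-injection cases and this trial has 4 or 5 vaccination visits.

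The cost is the removal of one paragraph. No new programming or data collection is needed, since the remaining rule is fully specified.
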